#### 12.4 Biologic response criteria CLL and SLL (78)

Given the favorable toxicity profile of curcumin and vitamin D3 in healthy adults and the intention to evaluate the efficacy of both agent to delay or prevent PD in patients with CLL/SLL, we also evaluated an additional response category termed "biologic response" among patients who did not meet standard NCI-WG criteria for CR and PR. The criteria for a biologic response were prospectively defined in a recent study of Polyphenon E, after discussion and approval of the NCI. Polyphenon E, very much like curcumin and vitamin D3, is the most active ingredient in green tea extract and it works through unique, noncytotoxic mechanisms. Biologic response was defined as a reduction in the absolute lymphocyte count (ALC) of > 20% from the pretreatment level that was sustained for at least 2 months or  $a \ge 30\%$  reduction in all palpable lymphadenopathy (78).

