#### 2.1 **Primary Objective**

To determine the overall response rate (ORR) based on NCI-WG criteria in CLL or the Cheson criteria in SLL. Will also examine biologic response rate (78); defined as at least 20% reduction of absolute lymphocyte count (ALC) that is sustained over 2 months or  $a \ge 30\%$  reduction in palpable lymphadenopathy using this regimen.

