#### 4.1 Inclusion Criteria

Patients must meet all of the following inclusion criteria to be eligible for enrollment:

4.1.1 Have a diagnosis of CLL based on peripheral blood flow cytometry and/or bone marrow aspiration and biopsy OR diagnosis of SLL based on lymph node or bone marrow biopsy. Patients with SLL need to have measurable disease (see section 12.2 for definition of measurable disease)

4.1.2 Subject, age  $\geq$  18 years (children are excluded from this study as CLL/SLL being exceptionally rare)

- 4.1.3 Performance Status (ECOG) 0-2 (see appendix A) ECOG PS = \_\_\_\_\_ Date: \_\_\_\_\_
  - \_\_\_\_\_\_ 4.1.4 Patients must have not received any prior treatment for CLL or SLL.

	4.1.6 Adequat	e bone marrow, rena	l, and hepatic function, per local reference
lat	ooratory ranges as fol	lows:	
	4.1.6.1 Absolute	e neutrophil count (A	NC) ≥ 1,500/mm3
	A	ANC=	Date:
	4.1.6.2 Platelet of	$count \ge 100,000/mm$	3
	P	latelets=	Date:
	4.1.6.3 Hemoglo	bin > 10 g/dL	
	Hinde Intensity.	Iemoglobin=	Date:
	4.1.6.4 Serum ci	reatinine $\leq 2.0$ g/dL	or calculated creatinine clearance
	(	$(CrCl) \ge 60mL/min$	Cockcroft-Gault method)
	C	Crcl =	Date:
			Date
	4.1.6.5 AST and	$ALT \le 2.5 \text{ x institu}$	tional upper limit of normal
	(	ULN) NST-	Date
	r A	AST= ALT=	Date:
	4.1.6.6 Bilirubir	n < 2.0  x ULN, unles	s subject has Gilbert's disease
	E	siiiruoin=	Date:
	4.1.6.7 Calcium	<10.1 mg/dL (corre	cted to serum albumin as follows:
	Corrected Calcin	um = (0.8 x (4 - patie))	ent albumin)) + serum Ca
	Corrected calciu	ım= Da	ite:
4.	1.7 Females will be	either postmenopau	sal for at least 1 year or surgically sterile
for	r at least 3 months (	OR Females of child	1-bearing potential must have a negative
pr	egnancy test at scre	ening and agree to	take appropriate precautions to avoid
pro	egnancy (double bar	rier method of birt	h control or abstinence) from screening
tin	ough 5 months arter	the last dose of freat	nent
4.1	1.8 Able to compreh	nend and willing to s	ign an Informed Consent Form (ICF)
4.1	1.9 Subjects must be	e off any steroids 7 c	ays prior to the initiation of treatment.
4.1	1.10 Subjects must be	e off any curcumin,	tumeric, or vitamin D supplements for 14
	days prior to the	initiation of treatme	nt.
4	1.11 Subjects must be	able to take oral me	dications
CASE 5913		20 of 7	4

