10.1.2 Rationale for Analysis

We plan to assess VDR at baseline and on D8, after 1 week of treatment with curcumin, and prior to starting vitamin D3 treatment to prove this. Quantitative intracellular measurement of VDR by flow cytometry, in peripheral blood mononuclear cells, has been performed, and validated, by other investigators before (86). The purpose of this analysis is exploratory/proof of concept. Subjects with SLL with no peripheral blood lymphocytosis will be excluded from this analysis.

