## 11.2 Calendar

Screening studies will studies are to be conducted within 30 days prior to administration of protocol therapy. Exception: Bone marrow biopsy, flow cytometry, cytometry, cytoegenetics, and interphase FISH performed up to 5 years prior to enrollment

Study Days	Pre- Study	Cycle 1 Day 1 b	Cycle 1 Day 8	Cycle 2 Day 1	Cycles 3- 6 Day 1	Cycles 7+ Day 1 f	End of Treatment	30 Day Follow Up i	Long term Follow- Up g,i
REQUIRED ASSESSMENTS									

r				1	1				
Informed Consent	Х								
Demographics	Х								
Medical History	Х								
Height	Х								
Weight	Х	Х	Х	Х	Х	Х	Х	Х	Х
Vitals (blood pressure,	Х	Х	Х	Х	Х	Х	Х	Х	Х
pulse, temperature, and									
respiratory rate)									
Physical Examination i	Х	Х		X	Х	Х	Х	Х	Х
Concomitant	Х	X		X	X	Х	Х	Х	
Medication									
Assessment									
ECOG PS	Х	X	X	X	X	Х	Х	Х	Х
Baseline Symptoms	Х	X							
Adverse Event			X	X	X	X	X	X	X
Assessment									
Peripheral blood flow	X								
cvtometry									
Peripheral blood	X								
cytogenetics and FISH									
CBC / diff / platelets i	X	X	X	X	X	X	X	X	Х
Serum Chemistry a, i	X	X	X	X	X	X	X	X	X
B-HCG women of	X	X					X		
childbearing potential									
Vitamin D 25(OH)	X	X*		X*	X*	X*	X*	X	
level									
DISEASE									
ASSESSMENT									
Lymph node	Х	X		X	X	Х	Х	Х	Х
measurement									
СТ	Х				Х				
chest/abdomen/pelvis c									
Bone marrow biopsy	Х								
(optional)									
MISC ITEMS									
Pill Diary		Х		X	X	X	Х		
TREATMENT									
Curcumin									
Vitamin D3									
CORRELATIVE									
STUDIES									
Pharmacokinetic		X	X	X					
Sampling d									
Flow cytometry e		Х	Х	X					
Ouality of life	X h	1		1	1	1	X h		
questionnaire									

**a:** Albumin, alkaline phosphatase, total bilirubin, bicarbonate, BUN, calcium, chloride, creatinine, glucose, potassium, total protein, SGOT [AST], SGPT [ALT], sodium. Calculated creatinine clearance will be done if creatinine and/or BUN are abnormal. **[UH: Order COMP2]** 

**b:** Cycle 1, Day 1 evaluations do not need to be repeated if screening evaluations were conducted within 2 weeks prior to administration of protocol therapy

c: In subjects with SLL who have ALC<5000 and non-measurable peripheral adenopathy

**d:** Plasma level of curcumin and vitamin D 25(OH)

e: For vitamin D receptor, NF-κB, and bcl-2, CLL patients only

f: For patients attaining a partial response or better

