## MEASUREMENT OF EFFECT

#### **12.1** Response Criteria for CLL; based on NCI-WG (107)

**Complete response** requires all of the following for a period of at least two months from completion of therapy:

- Peripheral blood lymphocytes (evaluated by blood and differential count) below 4 x 10^9/L (4000/\_L).
- Absence of significant lymphadenopathy (eg, lymph nodes >1.5 cm in diameter) by physical examination.
- No hepatomegaly or splenomegaly on physical exam;
- Absence of constitutional symptoms;
- Normal CBC as exhibited by polymorphonuclear leukocytes >  $1500/\mu$ L, platelets >  $100,000/\mu$ L, hemoglobin > 11.0 g/dl (untransfused)
- Bone marrow aspirate and biopsy must be at least normocellular for age, with less than 30% of nucleated cells being lymphocytes. Lymphoid nodules should be absent. If the marrow is hypocellular, a repeat determination should be performed after 4 weeks, or until peripheral blood counts have recovered. However, this time interval should not exceed 6 months after the last treatment.
- Patients who fulfill the criteria for CR after induction with the exception of a persistent cytopenia that is believed to be treatment related will be considered a partial response. Additionally, patients who fulfill the criteria of CR with exception of having bone marrow lymphoid nodules will be considered a partial response. Patients who fulfill the criteria of CR but declined having a bone marrow biopsy will be considered be in PR.

**Partial response** requires a > 50% decrease in peripheral lymphocyte count from pretreatment value, > 50% reduction in lymphadenopathy, and/or > 50% reduction in splenomegaly/ hepatomegaly for a period of at least two months from completion of therapy. All lymph nodes will be measured bi-dimensionally and the sums of these added to determine if 50% or greater reduction has occurred.

Additionally, these patients must have one of the following:

- Polymorphonuclear leukocytes > 1,500/µL or 50% improvement from pre-treatment value;
- Platelets >  $100,000/\mu$ L or 50% improvement from pre-treatment value;
- Hemoglobin > 11.0 g/dl (untransfused) or 50% improvement from pretreatment value.

**Progressive Disease** is characterized by any one of the following events:

- >50% increase in the products of at least two lymph nodes (at least one lymph node must be > 2 cm); appearance of new palpable lymph nodes.

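### Biologic response counts a fall in lymphocyte count from any starting value, in SLL as well as CLL, so a fall in an already low count can make a primary-endpoint responder

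*Combined protocol and SAP*

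**What the plan says.** Section 12.4 is titled "Biologic response criteria CLL and SLL". Its first arm reads "Biologic response was defined as a reduction in the absolute lymphocyte count (ALC) of > 20% from the pretreatment level", and a duration condition follows: the fall must persist for 2 months or more. The second arm is a reduction of at least 30% in palpable nodes, and either arm is enough. Section 2.1 repeats the blood arm ("reduction of absolute lymphocyte count (ALC) that is sustained over 2 months"), with the threshold given as at least 20% rather than more than 20%. Neither section names a minimum starting count.

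Section 14.1 defines the primary endpoint as biologic response plus CR plus PR. Section 14.2 defines clinical benefit for the futility rule as biologic response or better: 2 of the first 10 patients continue the trial, and more than 5 of 29 make the combination worth pursuing.

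Four other places bear on blood counts:

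- Section 11.2, calendar note c, prescribes CT "In subjects with SLL who have ALC<5000 and non-measurable peripheral adenopathy". (Section 11.1.1 words the CT rule with a negation. Either wording presupposes that ALC below 5,000 occurs in SLL.)
- Section 10.1.2, on the vitamin D receptor study in blood cells: "Subjects with SLL with no peripheral blood lymphocytosis will be excluded from this analysis". Section 10.2.2 says the same for NF-κB and bcl-2.
- Section 12.3 bases CR and PR in SLL on nodes, organs, imaging and marrow. No item is a blood count.
- Section 12.1 counts a lymphocyte rise of more than 50% as CLL progression only if it reaches at least 5,000/µL, and requires fewer than 4,000/µL for CR.

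**The concern.** A percentage fall in ALC indicates tumour burden when the count is raised by the disease. In an SLL patient without lymphocytosis, the same fall says little about disease that sits in nodes or marrow. Section 12.4 does not separate these cases. A patient starting at 2,000/µL is already below the 4,000/µL ceiling that Section 12.1 sets for a complete response in CLL, yet can still be scored as a new response.

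The rules are also asymmetric. The CLL lymphocyte progression criterion is shielded from movement at low counts by its 5,000/µL floor. The response criterion has no such shield.

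The decision thresholds are small. At stage I one such responder is half of the 2 needed to continue, and at the end one is a sixth of the 6 needed for a positive result.

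**Working it through.** **1. What the rule does to one patient.** Take an SLL patient with ALC 2,000 before treatment and 1,550 on treatment for 2 months, nodes unchanged. The fall is (2,000 − 1,550)/2,000 = 22.5%, which exceeds 20%. By Section 12.3 this patient is not in CR or PR. By Section 12.4 the patient is a biologic responder, and by Section 14.1 a primary-endpoint responder.

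**2. The plan's own design figures.** Inputs from Section 14.2: 10 patients at stage I, stop at 1 or fewer; 29 in total, fail at 5 or fewer; null 0.10, alternative 0.30.

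- P(stop at stage I) = P(Bin(10, p) ≤ 1). At p = 0.10: 0.9^10 + 10 × 0.1 × 0.9^9 = 0.349 + 0.387 = 0.736 (plan: 0.74).
- P(positive) = Σ over x = 2 to 10 of P(Bin(10, p) = x) × P(Bin(19, p) ≥ 6 − x). This gives 0.047 at p = 0.10 (plan: 0.05) and 0.805 at p = 0.30 (plan: 0.8).

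The stated design reproduces.

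**3. How often a flat count qualifies by chance.** Assumptions, none of them in the documents: no drug effect, lognormal within-person variation around a constant mean, independent readings, one baseline count, and six monthly counts (day 1 of cycles 2 to 6 and end of treatment). The documents do not say how many counts establish that a fall was sustained, so three readings are shown (simulation, 400,000 patients per setting).

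| Within-person CV | Three consecutive low counts | Two low counts 2 months apart | Three consecutive, mean of two baselines |
|---|---|---|---|
| 10% | 1.5% | 4.0% | 0.3% |
| 15% | 6.2% | 13.0% | 2.9% |
| 20% | 11.2% | 20.8% | 6.9% |
| 25% | 15.1% | 26.6% | 11.0% |

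The 2-month condition is already included. It does not remove chance responses, because one high baseline reading carries into every later comparison.

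**4. Does the rate depend on the starting level?** No. The criterion is relative and so is the assumed variation. Repeating the three-consecutive-count simulation with a mean ALC of 2,000, 6,000 or 30,000 gives about 1.5%, 6%, 11% and 15% each time.

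**5. Effect on the trial.** This needs a share of patients without lymphocytosis; 20% is assumed for illustration. There are two ways to combine the rates.

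- These patients respond only by chance (rate q) and all others at 10%: p = 0.8 × 0.10 + 0.2 × q. With q = 6.2%, 11.2% and 15.1%, p = 0.092, 0.102 and 0.110, and the type I error is about 0.034, 0.052 and 0.069, against 0.047 as designed.
- Chance responses come on top of a 10% true rate in the same patients. With q = 10%: p = 0.10 + 0.9 × 0.2 × 0.10 = 0.118. The type I error is then 0.089, and the chance of passing stage I rises from 0.264 to 0.334.

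The documents do not say which structure applies.

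**The case against.** **The figures do not isolate the missing floor.** This stands. By step 4, a patient above 5,000/µL with the same CV meets the ALC arm by chance just as often, and a 5,000/µL floor leaves that patient untouched. The percentages measure single-baseline noise and an undefined duration rule.

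**The null of 10% already applies to the composite endpoint.** This also stands. A reader might infer that the error rate is materially inflated. On the first calculation in step 5 it can fall below the designed 0.047; the larger values need chance responses added to a true 10% rate.

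**The criterion comes from an earlier trial and was discussed with and approved by the NCI** (Section 12.4). This carries some weight, but the title of that study in Section 15.0 names CLL only. Nothing in the documents shows that the criterion was set for SLL with unraised counts.

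Three further inferences are tempting but not supported:

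- That the protocol itself says the blood of these SLL patients carries no disease. Sections 10.1.2 and 10.2.2 exclude them without giving a reason.
- That CLL patients could also enter without a raised count. Item 4.1.1 ("Have a diagnosis of CLL based on peripheral blood flow cytometry and/or bone marrow aspiration and biopsy") names no count, but the available text goes from item 4.1.4 to 4.1.6, so the absence of a minimum cannot be asserted.
- That Section 12.1 ("Patients who fulfill the criteria of CR but declined having a bone marrow biopsy will be considered be in PR") lets an unchanged CLL patient be graded PR. This needs an unlikely patient and treats an unscheduled biopsy as a declined one. The summary table in 12.1 also asks for at least two tumour-load criteria plus one blood-function criterion for PR.

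**Conclusion.** The point holds as a gap in the definition of response, chiefly for SLL without lymphocytosis. Followed as written, Section 12.4 can score a primary-endpoint response, and one that counts at stage I, from a count that was not raised and with no change in nodes. This sits badly with the protocol's own SLL criteria, its blood correlatives and its progression floor.

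The size of the effect on the trial is unknown. It depends on the share of patients without lymphocytosis and on the within-person CV, and the documents give neither. The 1.5% to 15% range rests on CVs of 10% to 25%, one baseline and three consecutive low counts, and applies equally to patients with high counts. The argument for a floor is therefore that a fall in an unraised count does not measure the disease. It is not that chance responses are more frequent at low counts, nor that the type I error has been shown to exceed its stated level.

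**What to change.** In Sections 12.4, 2.1 and 14.2, score the ALC arm only in patients with a pretreatment ALC of at least 5,000/µL, the figure the protocol already uses in its progression and CT rules. Assess all other patients by nodes or imaging only. Since the nodal arm refers to palpable nodes, say explicitly how patients followed by CT are scored. Use one threshold wording in 2.1 and 12.4.

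Section 10.5 records that accrual closed on 4/12/2016, so this would be a change after accrual and cannot alter enrolment decisions already taken. Report the response rate under the definition as it now stands alongside the restricted one, and label which is which.

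The cost is wording and one additional reported rate. Baseline ALC and node measurements are already collected. A few patients lose one of two routes to response, and the reported rate may fall slightly. The floor does not reduce chance responses above 5,000/µL; that would need a definition of the baseline count and of how many readings make a fall sustained.

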#### 12.5 Duration of Response

#### **Duration of overall response:**

The duration of overall response is measured from the time measurement criteria are met for CR or PR (whichever is first recorded) until the first date that recurrent or progressive disease is objectively documented (taking as reference for progressive disease the smallest measurements recorded since the treatment started).

The duration of overall CR is measured from the time measurement criteria are first met for CR until the first date that progressive disease is objectively documented.

#### **Duration of stable disease:**

Stable disease is measured from the start of the treatment until the criteria for progression are met, taking as reference the smallest measurements recorded since the treatment started, including the baseline measurements.

#### **12.6 Progression-free survival (PFS)**

Progression-free Survival (PFS) is defined as the time from entry onto study until CLL/SLL progression or death from any cause. PFS is often considered the preferable endpoint in lymphoma clinical trials, especially those involving incurable histologic subtypes (e.g., follicular and low grade, mantle cell lymphoma). PFS reflects tumor growth and, therefore, occurs prior to the endpoint of overall survival. In addition, PFS is not confounded by the administration of subsequent therapy. Whether a prolongation of PFS represents direct clinical benefit or a surrogate for clinical benefit depends on the magnitude of the effect and the risk-benefit ratio of the therapy under investigation. Unlike survival, the precise date of progression is generally unknown. It may be defined as the first date of documentation of a new lesion or enlargement of a previous lesion, or the date of the scheduled clinic visit immediately after radiologic assessment has been completed. Where there is missing information, censoring of the data may be defined as the last date at which progression status was adequately assessed.

#### **12.7** Time to first cytotoxic treatment (TFCT)

CASE **5913** 52 of 74 Protocol Version 7 Dated **10/2/2018**  Time to first cytotoxic treatment (TFCT) is defined as the time from entry onto study until initiation of treatment with cytotoxic agents because of disease progression. As curcumin and vitamin D3 combination has the potential for delaying disease progression, or maintaining stable disease, TFCT is a clinically meaningful end-point of these patients.

## 13.0 RECORDS TO BE KEPT / REGULATORY CONSIDERATIONS

Adverse event lists, guidelines, and instructions for AE reporting can be found in Section 8.0 (Adverse Events: List and Reporting Requirements).

#### 13.1 Data Reporting

The OnCore Database will be utilized, as required by the Case Comprehensive Cancer Center, to provide data collection for both accrual entry and trial data management. OnCore is a Clinical Trials Management System housed on secure servers maintained at Case Western Reserve University. OnCore properly used is compliant with Title 21 CFR Part 11. Access to data through OnCore is restricted by user accounts and assigned roles. Once logged into the OnCore system with a user ID and password, OnCore defines roles for each user which limits access to appropriate data. User information and password can be obtained by contacting the OnCore Administrator at [contact].

This study will utilize electronic Case Report Form completion in the OnCore database. A calendar of events and required forms are available in OnCore.

## 13.2 **Regulatory Considerations**

The study will be conducted in compliance with ICH guidelines and with all applicable federal (including 21 CFR parts 56 & 50), state or local laws.

## 13.2.1 Written Informed consent

Provision of written informed consent must be obtained prior to any study-related procedures. The Principal Investigator will ensure that the subject is given full and adequate oral and written information about the nature, purpose, possible risks and benefits of the study as well as the subject's financial responsibility. Subjects must also be notified that they are free to discontinue from the study at any time. The subject should be given the opportunity to ask questions and allowed time to consider the information provided.

The original, signed written Informed Consent Form must be kept with the Research Chart in conformance with the institution's standard operating procedures. A copy of the signed written Informed Consent Form must be given to the subject.

#### 13.2.2 Subject Data Protection

In accordance with the Health Information Portability and Accountability Act (HIPAA), a subject must sign an authorization to release medical information to the sponsor and/or allow the sponsor, a regulatory authority, or Institutional Review Board access to subject's medical

information that includes all hospital records relevant to the study, including subjects' medical history.

13.2.3 Accessing Electronic Medical Records for University Hospitals Health System This study will access electronic medical records systems to obtain medical information for the subjects enrolled to this study.

In order to insure patient safety, investigators and study personnel must have up-to-the-minute health information for subjects enrolled to this study. Therefore, electronic medical records must be utilized to obtain medical information in a timely manner.

The following electronic systems will be used: Athena program to access scheduling information; UH Physician Portal to access lab results and physician notes; PCOSS LITE as necessary to locate archived medical records; COPATH to locate archived pathology records; PACS to access radiological imaging results; and MySecureCare (Sunrise Clinical Manager) to access some or all of the above information when this application is fully functional.

Access to these systems is required for the life of this research study.

Information obtained from electronic systems will be copied into the Seidman Cancer Center Clinical Trials Unit research chart and/or printed (lab results, physician notes, etc.) and stored in the research chart. Research charts are kept secure and destroyed according to UH policy.

Study data will be obtained by the PI, co-investigators, study coordinator, and/or data manager for this study via password-protected login.

